6. RESEARCH QUESTION AND OBJECTIVE(S)

This study aims to:

- i) gain an understanding of the clinical management of complicated influenza in ICU in Europe, including treatment patterns, monitoring the entry of new anti-influenza treatments and utilisation of diagnostic tests including resistance testing.
- ii) investigate the clinical effectiveness of IV zanamivir treatment in ICU patients with complicated influenza illness. Specifically:

Primary objective:

- To compare all-cause in-hospital mortality in a group of ICU-admitted patients with complicated influenza who receive treatment with IV zanamivir as part of their clinical care with all-cause in-hospital mortality in a propensity score-matched group of ICU patients who did not receive this therapy during the same influenza seasons and/or pandemic(s).

Secondary objectives:

- To understand, through the analysis of historical data, treatment patterns for ICU-admitted influenza patients and factors associated with NAI treatment.
- To estimate, in a time-dependent manner, the crude IV zanamivir treatment effect on all-cause in-hospital mortality in a group of ICU-admitted patients with influenza.
- To compare all-cause in-hospital mortality at 7, 10 and 14 days after IV zanamivir treatment initiation/matching in the two groups.

Exploratory objectives:

- To explore, through inverse-probability of censoring weighting (IPCW) analysis, the effect of non-persistence to exposure status in the analysis of the primary objective, above.
- To define the clinical course of disease for the IV zanamivir and comparator groups, categorized in 6 categories on an ordinal scale as described in Section 7.3.2.
 - The category of each patient on day 7, 10, 14 after IV zanamivir treatment initiation/matching
 - The change in category over time of each patient, from Day 1 to Day 14 after IV zanamivir treatment initiation/matching
- To compare the length of hospitalisation between the two groups
- To compare the length of ICU stay between the two groups
- To summarize associated complications of influenza (bacterial pneumonia, sepsis, myocarditis, encephalitis, acute respiratory distress syndrome, respiratory failure, bronchitis) in both groups.

7. RESEARCH METHODS

7.1. Study Design

The study will be a retrospective, observational, comparative chart review study conducted in ICU-admitted influenza patients in Europe. The collection of these data will be triggered by completion of the first seasonal influenza season following the grant of the marketing authorisation for IV zanamivir. There will be two parts to the study. The first stage (Part I) will involve the collection of historical data on patients from those influenza seasons which occurred prior to marketing authorisation. This part of the study, which aims to improve understanding of treatment patterns and to validate the assumptions for the comparative cohort, is timed to reflect current medical practice and to generate the most relevant data for comparison to the period following the grant of the marketing authorisation for IV zanamivir. If there are insufficient untreated patients, these historical data will assess whether the use of propensity score stratification or inverse-probability of treatment weighting (IPTW) would be appropriate. Similarly, if exposure to IV zanamivir is low, Disease Risk Score matching will be employed, as this technique has particular advantages when investigating newly marketed treatments with few exposures [Glynn, 2012]. Additionally, these historical data will serve to monitor the entry of new anti-influenza treatments, diagnostic tests and the regular use of resistance testing in future clinical practice. The second part (Part II) is the main comparative study with collection of data from ICU patients who were treated with IV zanamivir (IV zanamivir cohort) and those who did not receive this therapy at the point of matching (untreated cohort) during the same seasons/pandemic.

PART I: Historical Cohort

The data will be collected from a subset of eligible identified study sites (see Section 7.2). A dedicated research nurse(s) at each participating study site will complete study-specific electronic case report forms (eCRFs) for influenza patients who were admitted to ICU each year (see Section 7.3 for variables). Data collection will be for a pre-specified number of patients according to a pre-specified sampling frame (e.g. first 10 consecutive patients, based on admission date, per site and season).

PART II: Comparative Cohort

The collection of the comparative cohort data in this study will be triggered by completion of the first seasonal influenza season after the grant of the marketing authorisation for IV zanamivir in the EU. Once initiated, a dedicated research nurse(s) at each participating study site (see Section 7.2) will identify eligible patients from the hospital records and complete an eCRF for each patient (see Section 7.3 for variables).

7.2. Study Population and Setting

Study population

PART I: Historical Cohort

Inclusion criteria:

- Adults, adolescents, children and infants of all ages who were admitted to ICU with influenza illness.

Exclusion criteria:

- No informed consent given in countries where informed consent for retrospective chart reviews is mandated by local ethics/regulatory requirements.
- Prior treatment (within 30 days) with an investigational influenza drug therapy.

PART II: Comparative Cohort

Inclusion criteria:

- Adults, adolescents, children and infants of all ages who were admitted to ICU with influenza illness and treated with IV zanamivir as part of their routine medical care, treated with inactive antivirals or not treated at all.
 - Treatment may be initiated before or during ICU admission

Exclusion criteria:

- No informed consent given in countries where informed consent for retrospective chart reviews is mandated by local ethics/regulatory requirements.
- Prior treatment (within 30 days) with an investigational influenza drug therapy.

Setting

Hospitals are eligible to participate in this study if they fulfil all of the following criteria:

- Tertiary centre with ICU
- Ability to provide the variables of interest as described in Section 7.3.
- Ability for in-house testing for influenza type and sub-type by approved diagnostics

Hospitals in the European Union, UK, Norway and Iceland that participated in the Phase II and Phase III clinical trials, and the compassionate use program that meet the above criteria may be invited to join this study. These sites are situated in Belgium, the Czech Republic, Denmark, France, Germany, Greece, Hungary, Latvia, the Netherlands, Norway, Poland, Portugal, Slovakia, Spain and the UK. Additionally, ICU networks in France, Italy and the UK were identified through a literature search. A brief description of the networks can be found in the table below. If necessary, further hospitals will be identified through existing hospital networks that were set up for influenza surveillance or for post-pandemic data analyses. In the same literature review, networks in Spain [Cuevas Gonzalez-Nicolas, 2010] and the UK [Nguyen-Van-Tam, 2010] were identified as potentially interesting for follow-up.

Country	Network	Description
France	REVA-SRLF [Richard, 2012]	Network of 89 ICUs (25% of all ICUs in France) that reported ICU admissions (influenza vs non-influenza)
Italy	GiviTI [Bertolini, 2016]	Network of Italian 526 ICUs that report number of cases and reason for being in ICU, of which 359 are potentially relevant.
UK	USISS [Health Protection Agency, 2011]	Sentinel network of hospitals around the UK (from 36 randomly selected Acute Trusts) who report number of confirmed influenza cases hospitalised, and number of ICU admissions. Additionally, it includes a network of all Acute Trust ICUs in England who report admissions.

In addition to networks with ongoing reporting, two research networks that are not part of ongoing influenza surveillance were also identified at the time of writing this protocol. The first is a network of 13 university hospitals in Spain that was set up to investigate the relationship between oseltamivir and outcomes in hospitalised adults [Viasus, 2011]. The second is a European consortium (PRIDE) to perform an individual participant data meta-analysis on the effectiveness of antiviral use during the 2009 pandemic [Muthuri, 2014], which included data from 6,782 patients from European countries of which 90% originated from France, Spain and the United Kingdom.

7.3. Variables

Key clinical data that will be collected for both parts of this study are described below.

7.3.1. Exposure definitions

PART I: Historical Cohort

The aim of the historical cohort is to understand treatment patterns for ICU-admitted influenza patients and factors associated with treatment. Therefore, included patients will be those hospitalised with influenza and admitted to ICU.

PART II: Comparative Cohort

All subjects in the IV zanamivir treatment cohort are exposed to at least 1 dose of IV zanamivir. Subjects in the untreated comparator arm are not treated with IV zanamivir at the time of matching. In this approach, which is analogous to the intention-to-treat analyses employed in clinical trials, matched patients will retain their exposure status during the analysis regardless of future treatment status (IV zanamivir discontinuation/initiation in cases/matched comparators respectively). The effect of this potential exposure misclassification will be investigated (exploratory analysis; Section 7.7.2).

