7.6.3. Timings of Assessment during follow-up

The final data collection time for both the historical and comparative cohorts of the study is at hospital discharge, the latest available date before study withdrawal or loss to follow-up, or at day 28 after hospital admission if a patient has not been discharged or has been re-admitted to hospital within the 28-day study period.

The dedicated research nurse(s) at each site will check medical charts of discharged patients to identify eligible patients. [Table 2](#) below outlines for which times each (group of) variable(s) of interest will be collected.

Table 2 Proposed exposure and outcome assessment intervals

Data variable	At hospital admission	Before ICU admission	At/after ICU admission	Hospital discharge OR Day 28 post-treatment
Demographics	X			
Influenza diagnostics/details (e.g. influenza strain/type, diagnostic test)	X			
Other risk factors (confounders/effect modifiers from Section 7.3.3)	X	X	X	
In-patient IV zanamivir treatment	X	X	X	X
Admission to critical care facilities (e.g. ICU/high dependency unit [HDU])	X		X	X
Ordinal scale clinical outcomes	X	X	X	X
Mortality in hospital		X	X	X

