7.7. Data analysis

7.7.1. Essential analysis

All analyses will be performed in SAS 9.4. Descriptive analyses will be performed with continuous variables expressed as means with 95% confidence intervals or medians and ranges, as appropriate for the data distribution. Categorical variables will be expressed as frequency or proportion of patients in each category.

The sub-sections below are an outline of the types of analyses that are currently being considered. A detailed statistical analysis plan will be written before data collection for the comparative cohort starts.

PART I: Historical Cohort

A logistic regression analysis will be performed to identify factors associated with anti-influenza treatment versus no anti-influenza treatment. If sufficient data are available, the analysis will be repeated for IV zanamivir.

PART II: Comparative Cohort

Propensity scores will be derived from the predicted probability of IV zanamivir treatment estimated in a multivariable pooled logistic regression model with treatment/no treatment fitted as the binary outcome and the covariates listed in Section 7.3.3 above specified as explanatory variables. Treatment and exposure data will be captured separately for the pre- and post-ICU periods as per Section 7.6.3, and models will be stratified by season (to control for differences in severity) and by time since illness onset to facilitate appropriate matching. Standardised differences will be calculated to assess the balance achieved in the matched sample [Austin, 2011a]. If an insufficient number of matched pairs are obtained, alternative approaches e.g. propensity score stratification or inverse-probability of treatment weighting (IPTW) will be considered and the analysis modified accordingly [Cullen, 2009; Austin, 2011a]. Similarly, if only a small number of patients are exposed to IV zanamivir then a Disease Risk Score-match approach will be applied [Glynn, 2012]. For analysis of within-hospital mortality fitted as the binary outcome, the same method will be applied.

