If there are sufficient data, propensity score-matched samples will be created to compare: early (≤ 2 days from symptom onset to treatment initiation) versus late IV zanamivir treatment (> 2 days from symptom onset to treatment initiation); early IV zanamivir treatment versus no treatment; late IV zanamivir treatment versus no treatment. Analyses will also be conducted in the subset of mechanically-ventilated patients, and, if sufficient data are available, an analysis will be conducted on patients infected with influenza viruses where resistance is confirmed. If numbers are sufficient, further stratified analyses will be performed for adults and children (aged < 16 years) as well as for immunocompromised patients.

Following matching, patients will accrue time-at-risk from ICU admission (for IV zanamivir patients who initiated prior to ICU admission), treatment initiation (for IV zanamivir patients who initiated in the ICU) or ICU admission (comparator patients); as the study is conducted among ICU-admitted patients, person-time prior to ICU admission is immortal. Patients will be followed up until they experience the event of interest (death) or they are censored (the earlier of hospital discharge or 28 days post treatment/matching [as applicable]). For the secondary objectives described below censoring will be modified as appropriate (7, 10 or 14 days post treatment/matching).

Primary objective: all-cause in-hospital mortality to end of follow-up

A matched Cox regression analysis will be performed to estimate the association between IV zanamivir treatment and mortality during hospital stay. The treated vs. untreated groups will be compared to obtain the hazard ratio for in-hospital survival. Kaplan-Meier plots will be produced for graphical comparison of survival in the two groups.

Secondary objective: crude all-cause in-hospital mortality to end of follow-up

A crude estimate of the hazard ratio, based on the unmatched sample, will also be obtained using a time-dependent Cox regression model stratified by season, to control for differences in severity.

Secondary objective: All-cause in-hospital mortality at Day 7, 10 and 14

A regression analysis, similar to the primary analysis, will be performed on available mortality data at Day 7, 10 and 14 post treatment/matching.

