7.7.2. Exploratory analysis

Inverse Probability of Censoring Weighted (IPCW) Analysis

The proposed matching strategy seeks to minimise bias by not utilising future information to define exposure status [Hernan, 2016]. Accordingly, patients who are matched as controls may go on to receive IV zanamivir and treated patients may discontinue IV zanamivir. To examine the effect of this potential exposure misclassification, if observed to some ($\geq 10\%$) degree, (IPCW) analysis will be performed for the primary objective analysis. Patients who do not persist to their exposure status will be censored at the time of non-persistence, and stabilised weights – generated from a pooled logistic regression model with non-persistence fitted as the outcome variable and the parameters described in Section 7.3.3 included as explanatory variables – will be utilised in a weighted pooled logistic regression analysis of the effect of IV zanamivir treatment on all-cause within-hospital mortality.

Ordinal Scale at Day 7, 10 and 14

A proportional odds regression model will be fitted to estimate the odds of different categories of the ordinal scale at Day 7, 10 and 14, and their 95% confidence intervals, in the IV zanamivir group compared with the untreated group. Results will be presented for two levels of adjustment: (i) unadjusted (i.e., crude comparison) and (ii) using propensity score stratification with additional adjustment for ICU ventilation on Day 1, inpatient antibiotics and systemic corticosteroids. Patients will be assigned to the point on the ordinal scale based on the information for that day and not for the period up to and including that day (e.g. 0-7, 0-10, 0-14 days).

Length of hospital/ICU admission

Matched t-tests, or alternative non-parametric tests, will be performed to compare length of hospital stay and length of ICU admission between IV zanamivir and no IV zanamivir treatment patients (and, if sufficient data exist, by early/late treatment).

Associated complications

Descriptive analyses of the proportion of each treatment group with associated complications of influenza (bacterial pneumonia, myocarditis, encephalitis, sepsis, acute respiratory distress syndrome, respiratory failure, bronchitis) during ICU stay will also be reported.

For optimal comparability, the primary and secondary analyses will be repeated using the following definitions, which are similar to what was used in the Phase 3 clinical trial:

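### No rule requires a comparator's influenza to have been recognised by the matching day, so the primary hazard ratio can be biased in either direction

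*Protocol*

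**What the plan says.** Section 7.3.1 sets the comparator condition for Part II: "Subjects in the untreated comparator arm are not treated with IV zanamivir at the time of matching". Section 7.2 sets the population: patients "who were admitted to ICU with influenza illness and treated with IV zanamivir" in routine care, or "treated with inactive antivirals or not treated at all". It gives no date or day by which influenza must have been tested for, suspected or diagnosed.

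Cases are found from completed records. Under Section 7.6.3 the research nurse "will check medical charts of discharged patients to identify eligible patients". Table 2 in that section schedules influenza diagnostics at hospital admission.

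The safeguard in Section 7.7.2 concerns exposure: "The proposed matching strategy seeks to minimise bias by not utilising future information to define exposure status". It does not mention eligibility.

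Section 7.7.1 stratifies the propensity models by season and "by time since illness onset to facilitate appropriate matching". Time at risk starts at "treatment initiation (for IV zanamivir patients who initiated in the ICU) or ICU admission (comparator patients"; treated patients who began before the ICU also start at ICU admission. The covariates in Section 7.3.3 include symptom duration, presentation at admission and other antivirals, but no date of first suspicion or first positive sample.

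**The concern.** The two arms have different entry conditions. A clinician who gives IV zanamivir must already know or suspect influenza, so every treated patient was recognised, alive, before the first dose. This is an inference from what the treatment is for, not a rule written in the protocol. A comparator has no matching condition. The completed chart may show influenza that was not known on the matching day, and nothing in Sections 7.2 or 7.3.1 stops that patient from serving as a comparator on that day.

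Such patients could not yet have been candidates for treatment. They are most likely to sit in the wholly untreated group, because a patient on an inactive antiviral has usually been suspected already.

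The primary comparison is at stake. A comparator first identified from a result available only at or after death is a death by construction, which favours IV zanamivir. A comparator recognised later while alive had to survive until recognition. With the comparator clock starting at ICU admission, that guaranteed survival counts as follow-up and works against IV zanamivir.

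**Working it through.** **Inputs from the protocol (Section 7.5).** Untreated mortality 12% (range 5% to 25%), 1:1 ratio, 450 per arm, odds ratio 0.5, 80% power, 5% level, continuity correction.

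**Assumed inputs.** The documents give no share of late or post-mortem recognition. Let f be the share of comparators in the late-recognised group and m their mortality.

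**1. The plan's own figure.** Odds at 12% are 0.12/0.88 = 0.1364. Half of that is 0.0682, so treated mortality is 0.0682/1.0682 = 6.38%. A two-sided two-proportion calculation with continuity correction gives 449 per arm against the stated 450 (415 without the correction). The 12% and 450 are therefore a sound base for illustration.

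**2. Entry conditions side by side.**

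| | Treated | Comparator |
|---|---|---|
| Illness | ICU admission with influenza | Same |
| Treatment | At least one dose of IV zanamivir | None at matching; inactive or no antivirals |
| Recognised by index day | Yes, implied by the first dose | Not required |
| Clock start | ICU admission, or initiation if begun in ICU | ICU admission |

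**3. Towards benefit.** The drug has no effect and true mortality is p in both arms. Late cases are all recognised at or after death (m = 1). Comparator mortality is p(1 − f) + f. The share of comparator deaths that are such cases is f divided by that figure. With f = 2%, or 9 of 450 comparators:

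- p = 12%: 0.12 × 0.98 + 0.02 = 13.76%. Odds ratio (0.12/0.88)/(0.1376/0.8624) = 0.1364/0.1596 = 0.85. Share of deaths 0.02/0.1376 = 14.5%. An unmatched two-proportion test with 450 per arm would show a falsely significant benefit in about 12% of studies, against a nominal 2.5%.
- p = 5%: comparator mortality 6.9%, odds ratio 0.71, share of deaths 0.02/0.069 = 29.0%.
- p = 25%: comparator mortality 26.5%, odds ratio 0.925, share of deaths 0.02/0.265 = 7.5%.

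**4. Against the drug.** Take p = 12%, f = 10% recognised late but alive, m = 6% (half of 12%). Comparator mortality is 0.12 × 0.90 + 0.06 × 0.10 = 11.4%. Odds ratio 0.1364/(0.114/0.886) = 0.1364/0.1287 = 1.06.

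**5. Time-to-event check.** A Cox simulation of an ineffective drug used the protocol's clocks, with mortality of 12% or 25%. Half the patients were recognised at ICU admission and the rest after a mean of 3 or 7 days. The true hazard ratio is 1.

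| Unrecognised deaths later identified as influenza | Constant hazard | Front-loaded hazard |
|---|---|---|
| None | 1.06–1.14 | 1.03–1.08 |
| Half | 0.99–1.00 | 0.87–0.91 |
| All | 0.88–0.95 | 0.73–0.82 |

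Two corrections were tried. Removing the post-mortem cases but leaving the comparator clock at ICU admission still gave 1.03 to 1.14. Admitting only comparators recognised alive before matching and starting both arms at the same recognition time gave 0.99 to 1.01 in every scenario.

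**The case against.** The strongest reply is that the protocol presupposes early diagnosis. Admission to ICU with influenza can be read as influenza known at that point. Table 2 places diagnostics at hospital admission, and Section 7.2 limits sites to those with in-house influenza typing. Post-mortem diagnosis is not mentioned anywhere. This makes the gap smaller but does not close it. The eligibility phrase names the illness, not when it became known, and Table 2 is a collection schedule, not an entry rule. Two chart reviewers could classify the same late-diagnosed patient differently.

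A second reply is that the covariates in Section 7.3.3 carry part of the information. Presentation at admission, symptom duration, other antivirals and the reason for limited options are plausible partial proxies for recognition. That stands: it would be too strong to say that matching removes none of the bias. But none of them dates recognition, and the weighted analysis in Section 7.7.2 deals with later switching, not with entry.

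A third reply is that the SAP, eCRF and data management plan are not shown, and date fields often belong there. That also stands, so it cannot be said that the dates will not be captured. Eligibility, comparator definition and clock start, however, are fixed in this protocol. Section 7.9 does acknowledge possible residual confounding by indication and has Part I assess whether a comparator group is feasible, but neither step sets an entry rule.

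**Conclusion.** The point holds as a gap in the eligibility rule with bias of uncertain sign. The plan keeps future information out of exposure status but not out of comparator eligibility, and its clocks add to the problem.

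The size is unknown. The illustrations (odds ratio about 0.85 one way, about 1.06 the other) rest on assumed shares, 12% mortality in both arms and an unmatched binary comparison, whereas the primary analysis is a matched Cox model.

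A reader might infer that the design makes an ineffective drug look protective. The documents do not support that as a general statement: it depends on how many cases first identified at or after death enter relative to those recognised late while alive. In the simulation the hazard ratio ran from 0.73 to 1.14.

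A reader might also take a large false-positive rate from the same arithmetic. At f = 5% the odds ratio is 0.70 and the chance of a falsely significant benefit is 47%. But that needs 0.05/0.164 = 30.5% of comparator deaths to have been first recognised at or after death. Nothing in the documents supports such a share, so it should not be quoted as an expected size.

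**What to change.** - **Sections 7.2 and 7.3.1:** a patient may serve as comparator on a given day only if influenza was confirmed, or recorded as suspected (test requested or influenza named in the notes), on or before that day. Exclude cases first recognised after death.
- **Data collection:** record the date of first suspicion and the date of the first positive sample.
- **Propensity model or matching:** include time since recognition alongside time since illness onset.
- **Section 7.7.1:** start each comparator's time at risk at the matched index day, so that it aligns with the treated patient's clock. For treated patients who began before the ICU, the index remains ICU admission in both arms. The clock change is needed as well as the eligibility rule, because removing post-mortem cases alone left a bias against the drug in the simulation. The simulated correction started both arms at recognition. A matched index day follows the same principle but was not simulated separately.

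The cost is one or two date fields, a few sentences of protocol text and a somewhat smaller comparator pool. That last cost matters because Section 7.9 already expects that untreated patients may be few; Part I can check it. The planned 450 per arm does not change.
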